
Study Design
	
This Investigator-initiated, Treatment of High-Risk Prostate Cancer Guided by Novel Diagnostic Radio- and Molecular Tracers (THUNDER) study will be conducted in subjects with high-risk localized or locally advanced PCa. The study contains both a randomized Phase 3 treatment intensification study, and a treatment de-intensification non-randomized Phase 2 study. The aim of the THUNDER study is to improve the outcome of high-risk PCa by improved risk stratification using novel radiotracers (PSMA PET/CT) and a genomic classifier (Decipher) and subsequent treatment adaptation.
 
The hypothesis for the study is that treatment intensification based on a positive PSMA PET/ CT or Decipher high score (<math>> 0.6</math>) improves time to new metastases detected on PSMA PET/ CT in high-risk PCa.
 
In patients who are PSMA PET/ CT negative for regional or distant metastases with a low/ intermediate Decipher score (<math>\leq 0.6</math>), it is hypothesized that treatment de-intensification will improve patient quality of life while maintaining a good oncological outcome.
 
The study will be conducted at multiple centers across Europe.
 
Participation in the study will comprise a screening period, where the screening assessments must be completed before subjects are enrolled and randomized (if applicable). Eligible, consenting subjects will then undergo treatment according to their assigned study phase and treatment group, to occur over up to 96 weeks (24 months) with a post-treatment follow-up period to monitor safety and efficacy. The study will be closed 7 years from the time of randomization of the first subject.
 
The screening, treatment, and follow-up schedules are the same for both the Phase 3 and Phase 2 parts of the study, as delineated in the Schedule of Events (SOE).
 
Phase 3 Treatment Intensification Study: Patients with High-risk PCa and Positive PSMA PET/ CT and/ or Decipher high (<math>> 0.6</math>)
 
Approximately 360 evaluable patients with high-risk localized or locally advanced PCa, with PSMA positive non-localized disease or a Decipher high score (<math>> 0.6</math>) will be enrolled to the Phase 3 study. Subjects with negative PSMA PET/ CT who subsequently return a high Decipher score will also be enrolled and randomized into the Phase 3 study. All Phase 3 subjects will be randomly assigned in a 1:1 ratio to receive darolutamide plus LHRHA, or darolutamide matched placebo plus LHRHA, for up to 96 weeks (24 months). All Phase 3 subjects will also receive primary SOC RT. Subjects in Phase 3 should be commenced on an LHRHA and darolutamide or placebo within 14 days after randomization (unless started earlier) plus SOC RT for a period of approximately 1-8 weeks starting at 8–24 weeks after enrollment and randomization. Randomization of Phase 3 subjects will be stratified by 1 versus <math>> 1</math> high-risk features, N1 versus M1 PSMA positive versus PSMA negative disease, Decipher low/ intermediate versus high score, start of ADT within 4 weeks prior to randomization and clinical trial site.
 
Phase 2 Treatment De-intensification Study: Patients with High-risk PCa and Negative PSMA PET/ CT and Low/ Intermediate Decipher (<math>\leq 0.6</math>)
 
Approximately 133 evaluable patients determined to have localized PCa by PSMA PET/ CT (PSMA negative) with a low/ intermediate Decipher test score (<math>\leq 0.6</math>) will enter the non-randomized, Phase 2, single treatment arm, de-intensification study. As noted above, subjects with localized PCa by PSMA PET/ CT who return a high Decipher score (<math>> 0.6</math>) will be enrolled and randomized into the Phase 3 study. All Phase 2 study subjects will receive darolutamide for the study duration for up to 96 weeks (24 months) and primary SOC RT for a period of approximately 1-8 weeks starting at 8–24 weeks after enrollment.

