	
Decipher score
 
 
a. Subjects who have a negative PSMA PET/ CT and a tumor with a low/ intermediate Decipher score (<math>\leq 0.6</math>) will be eligible to enter the non-randomized Phase 2 study.
 
b. Subjects who have a negative PSMA PET/ CT and a tumor with a high Decipher score (<math>> 0.6</math>) will be eligible to be randomized to either arm of the Phase 3 study.
 
c. In subjects with positive PSMA PET/ CT, the Decipher score will not determine the treatment allocation.
 
 
 
6. Willingness to undergo SOC RT and long-term ADT (treatment with darolutamide and/ or LHRHA)
 
7. Subject is able and willing to provide written informed consent, which includes compliance with and ability to undergo all study procedures and attend the scheduled follow-up visit/s per protocol.
 
8. Subject must be over 18 years of age.
 
9. Subject able to swallow whole study drug tablets.
 
10. To avoid risk of drug exposure through the ejaculate (even men with vasectomies), subjects must use a condom during sexual activity while on study drug and for 3 months after the last administration of study treatment. Donation of sperm is not allowed during the treatment phase and for 3 months after the last administration of study treatment.
 
11. Adequate organ function determined by the following local laboratory values:             
 
a. Adequate bone marrow function: Hemoglobin <math>\geq 100</math> g/L, white cell count (WCC) <math>\geq 4.0 \times 10^9/L</math>, absolute neutrophil count (ANC) <math>\geq 1.5 \times 10^9/L</math> and platelets <math>> 100 \times 10^9/L</math>
 
b. Adequate renal function: calculated creatinine clearance <math>> 30</math> mL/min (Cockcroft-Gault)
 
c. Adequate liver function: alanine aminotransferase (ALT) <math>< 2</math> x upper limit of normal (ULN) and total bilirubin <math>< 1.5</math> x ULN, (or if total bilirubin is between 1.5 to 2 x ULN, they must have a normal conjugated bilirubin)
 
d. Testosterone levels <math>> 50</math> ng/dL
 
 
 
 
Exclusion criteria: A subject who meets any of the following criteria must be excluded from the study:
 
 
1. Definitive radiologic evidence of metastatic disease outside of the pelvic nodes (M1a, M1b or M1c) on conventional imaging (i.e., bone scan, CT scan, MRI)
 
2. PCa with predominant non-adenocarcinoma features (sarcomatoid or spindle or neuroendocrine small cell or squamous cell components or other non-adenocarcinoma)
 
3. Prior pelvic radiotherapy
 
4. Contraindications for pelvic radiotherapy
 
5. Contraindications for ADT (treatment with darolutamide and/ or LHRHA)
 
6. Contraindications or known allergy to PSMA PET/ CT tracers.
 
7. Prior local therapy for PCa (e.g., radical prostatectomy, high-intensity focused ultrasound [HIFU], cryotherapy). Subjects with previous transurethral resection of the prostate (TURP) or Millin prostatectomy are eligible for participation
 
8. Prior systemic therapy for PCa, except for patients with a positive PSMA PET/ CT staging who are allowed to start with ADT if no more than 4 weeks prior to randomization.
 

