	
number, we can extrapolate the number of patients needed to be screened as only 40% of patients will have a positive PSMA scan, based on the Australian ProPSMA study (Hofman 2020) and we hypothesize that 55% of patients with a negative PSMA PET would still have a Decipher high score.
 
The following assumptions apply:
 
Based on the data from randomized trials including high-risk PCa we estimate that the 5-year FFS is 70%. In 40% of cases, a PSMA PET will detect disease outside the prostate with approximately 20% having N1 disease and 20% M1 disease. In another 30% of cases, the PSMA will be negative, but the Decipher score will still be > 0.6. We expect that the patients with a positive PET outside the prostate have a higher failure rate with current standard treatment approaches with FFS of 60% and 40% for N1 and M1 disease, respectively, or 50% combined. We expect patients with a negative PET, but Decipher high score will have a FFS of 75%. From these data, it is estimated that the combined PSMA positive or Decipher high group has a 5 year FFS of 61%. We hypothesize an increase to 76% with the addition of darolutamide.
 
Assuming proportional hazards (and for the translation from number of events to number of patients also assuming exponential FFS), the calculations were made in Power Analysis and Sample Size (PASS) software and confirmed with simulations in R.
 
 
• Accrual: 3 years
 
• Additional follow-up: 3.5 years
 
• Total duration: 3 + 3.5 = 6.5 years
 
• 5 year FFS in control arm: 61 %
 
• 5 year FFS in experimental arm 76 %
 
• Hazard ratio: 0.56
 
• Two-sided alpha of 0.05
 
• Power of 80%
 
 
With these settings, the total number of events needed is 96. For this – assuming the proportion PSMA positive and Decipher high as presented before – an estimated 306 patients need to be enrolled. With an expected dropout of 15%, this results in a requirement for 493 patients in total to be screened. In simulations, the power of the trials proved to be robust against misspecification of the PSMA positive and Decipher high proportions in the screened population – when using the number-of-events-based stopping rule.
 
Phase 2:
 
The primary endpoint for this Phase 2 study will be to detect a clinically meaningful difference in the EPIC sexual and hormonal subdomain as detected at 12 months. A comparison will be made between the patients recruited in this single arm phase 2 trial with those recruited in the phase 3 trial. This will result in comparing patients receiving either darolutamide monotherapy versus standard of care ADT and ADT plus darolutamide. We aim to measure the scores on a yearly basis to monitor late effects. We expect the baseline quality of life at inclusion will be comparable for the phase 2 and phase 3 patients as they only differ in their PSMA PET-CT result and Decipher score. Consequently, only the treatment allocation influences the quality of life.
 
Assuming an 11 points difference in the sexual domain, a standard deviation of 31.1 (based on PROSTQA) and 10% dropout/ non-compliance/ consent withdrawal incorporated group sizes of 122 (Decipher low) and 153 (SOC) and 153 (SOC+darolutamide), the estimated power is 83% (based on a t-test assuming equal variances – as the primary analysis is an analysis of covariance (ANCOVA) with group and baseline score as predictors, this can be assumed a lower bound). This 11 point difference is considered as the threshold of a minimally important difference for the sexual domain.
 
Analysis of the Primary Endpoints

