--	---

	
Phase 3: ppMFS is defined as the time from randomization to the date of detection of at least 1 new PSMA-PET-positive distant lesion compared with the baseline scan or date of death from any cause. Event-free patients are censored at their last known follow-up date. ppMFS will be estimated using the Kaplan-Meier method. For the Phase 3 intensification study, the primary analysis comparing treatment arms will be a stratified log-rank test (stratified according to the randomization-strata).
 
Phase 2: EPIC mean changes in subdomain scores over time will be compared, both for change from baseline and absolute scores. The primary analysis will be an ANCOVA with group and baseline value as predictors. Given that at 1 year, the expected mortality is rather low, the primary analysis will treat deceased patients as having missing data under missing at random (MAR). As sensitivity analysis, the missing data for deceased will be imputed by worst score. An additional sensitivity analysis using trimmed means will be performed.

--	--

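### Only Phase 3 comparators may start ADT before randomization, so their baseline EPIC can already reflect treatment, and the Phase 2 primary ANCOVA has no term for it

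*Protocol*

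**What the plan says.** All references are to the protocol Synopsis.

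- **Eligibility Criteria, exclusion 8** bars prior systemic therapy for prostate cancer, with one exception: "patients with a positive PSMA PET/ CT staging who are allowed to start with ADT if no more than 4 weeks prior to randomization".
- **Eligibility Criteria, inclusion 4 and 5** send every PSMA-positive patient to Phase 3. Phase 2 takes "Subjects who have a negative PSMA PET/ CT and a tumor with a low/ intermediate Decipher score" of at most 0.6, so the exception can never apply there.
- **Study Design, Phase 3** has LHRHA and study drug begin "within 14 days after randomization (unless started earlier"), and lists among the stratification factors "start of ADT within 4 weeks prior to randomization and clinical trial site".
- **Statistical Methods, Sample size rationale, Phase 2** sets up the non-randomized contrast: "A comparison will be made between the patients recruited in this single arm phase 2 trial with those recruited in the phase 3 trial". It continues: "We expect the baseline quality of life at inclusion will be comparable for the phase 2 and phase 3 patients". The reason given is that PSMA PET-CT result and Decipher score are the only differences between the phases, from which it concludes that treatment allocation alone drives quality of life.
- **Analysis of the Primary Endpoints, Phase 2** fixes the model: "The primary analysis will be an ANCOVA with group and baseline value as predictors". Comparisons of change from baseline and of absolute scores are also planned.
- **Eligibility Criteria, inclusion 11d** requires testosterone above 50 ng/dL and states no exemption for patients already on ADT.

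**The concern.** An ANCOVA of this kind treats the baseline score as a pre-treatment measurement. In Phase 2 it must be one, because no prior systemic therapy is allowed. In Phase 3 it need not be. Screening has only to be finished before enrollment and randomization, and nothing in the text available requires the EPIC to precede the first ADT dose. For a patient already on ADT when approached, a pre-ADT EPIC cannot be obtained at all.

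Where this happens, the model pairs a lowered comparator baseline with an untreated Phase 2 baseline of the same value. It then credits part of the LHRHA effect to baseline. Stratifying on early ADT balances the two Phase 3 arms against each other but does nothing for Phase 2 versus Phase 3.

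At stake is the estimated quality-of-life gain from omitting LHRHA, which is read against fixed thresholds of 11 points (sexual) and 5 points (hormonal).

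**Working it through.** **1. The plan's own figure.** Inputs: "Assuming an 11 points difference in the sexual domain, a standard deviation of 31.1 (based on PROSTQA"), groups of 122 and 153 with dropout already incorporated, and two-sided alpha 0.05 (stated for Phase 3, assumed here). A two-sample t-test gives 82.7% power and the normal approximation 83.0%. The stated 83% reproduces.

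**2. Share of comparators that could be affected.** The sample size rationale gives 40% PSMA-positive, and 55% Decipher-high among the PSMA-negative. PSMA-positive share of Phase 3 = 0.40 / (0.40 + 0.60 × 0.55) = 0.40 / 0.73 = 55%. With the protocol's rounded 30% for the second group it is 0.40 / 0.70 = 57%. In Phase 2 the share is 0%.

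**3. Bias.** Assume that early starters have the same 12-month score as other comparators and differ only in a baseline lowered by *d* points. With *p* the share of comparators affected and *b* the slope of 12-month on baseline score:

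adjusted difference = 11 − *b* × *p* × *d*, where *p* = 0.548 × share of PSMA-positive patients affected.

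The share, *d* and *b* are assumptions; the protocol gives none of them.

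| Case | *b* | Share | *d* | *p* | Loss in ANCOVA | Difference left | Loss in change from baseline (*p* × *d*) |
|---|---|---|---|---|---|---|---|
| Low | 0.5 | 50% | 5 | 0.274 | 0.7 | 10.3 | 1.4 |
| Middle | 0.6 | 75% | 10 | 0.411 | 2.5 | 8.5 | 4.1 |
| High | 0.7 | 100% | 15 | 0.548 | 5.8 | 5.2 | 8.2 |

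**4. Power under the planned model.** With equal variances at both times the slope equals the correlation, so the residual SD is 31.1 × √(1 − *b*²), and SE = residual SD × √(1/122 + 1/153).

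| Case | Residual SD | SE | Power, no bias | Power, with bias | Power, indicator added |
|---|---|---|---|---|---|
| Low | 26.9 | 3.27 | 92% | 88% | 87% |
| Middle | 24.9 | 3.02 | 95% | 80% | 88% |
| High | 22.2 | 2.70 | 98% | 49% | 90% |

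Simulated ANCOVA (4,000 runs per case) agreed with the biased-power column to within 2 percentage points. The last column is simulated: adding a 0/1 term for ADT started before the baseline EPIC returned estimates of 11.0, 10.9 and 11.0 points.

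**5. Hormonal domain.** The protocol gives no SD, so power cannot be computed. Purely as illustration, a 5-point baseline drop would cost 0.5 × 0.274 × 5 = 0.7 to 0.7 × 0.548 × 5 = 1.9 of the 5-point threshold.

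**The case against.** The strongest reply is that the key condition is not demonstrated. The bias exists only if the baseline EPIC follows ADT, and assessment timing belongs to the Schedule of Events, which is not in the text available. Completing screening before randomization sets a latest date and does not show that EPIC comes after ADT. This stands. A reader might infer that baseline comparability fails by design; the document supports only that it can fail.

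Inclusion 11d also counts. Read literally, an early starter qualifies only if testosterone was measured before ADT, or had not yet fallen to 50 ng/dL. Either way, fewer patients would combine prolonged ADT with a post-ADT baseline, so the high case is hard to sustain. A drop of 10 to 15 points within 4 weeks would also be about as large as, or larger than, the whole 11-point difference assumed at 12 months.

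Three further inferences do not hold:

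- **That power falls from 83% to about 78%, 62% or 28%.** Those values put the biased differences into an unadjusted t-test with SD 31.1 while using ANCOVA slopes for the bias. The protocol itself calls the t-test figure a lower bound for the ANCOVA.
- **That covariate adjustment cannot repair the problem.** Baseline alone cannot, but an early-ADT indicator beside it does.
- **That stratifying on early ADT proves many early starters are expected.** No share is given.

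Finally, the bias runs against the trial's hypothesis, so it would not manufacture a benefit. That is true, but an estimate pulled towards zero is still wrong when it is read against a fixed threshold.

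**Conclusion.** The point holds in conditional form. The text allows ADT before baseline in the comparator and forbids it in Phase 2. This contradicts the statement that the phases differ only in PSMA result and Decipher score, whatever the Schedule of Events says. The primary model has no term for the difference.

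If early starters complete EPIC after ADT begins, the adjusted sexual-domain difference is attenuated by slope × affected share × drop. That is 0.7 to 5.8 of 11 points over the assumed range, with the upper end unlikely and a loss below 1 point quite possible. The change-from-baseline comparison takes the full drop without the slope factor. PSMA-negative, Decipher-high comparators, about 45% of Phase 3, are unaffected. If the Schedule of Events or the SAP already places EPIC before any ADT, the bias disappears and only the comparability statement needs correcting.

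**What to change.** 1. State that the baseline EPIC is completed before the first ADT dose wherever the patient has not yet started, and record ADT status at the baseline EPIC for everyone. This must be done prospectively, since a missed pre-ADT baseline cannot be recovered.
2. Add an indicator for ADT started before the baseline EPIC to the Phase 2 primary ANCOVA. The stratification factor already captures early ADT relative to randomization; what is needed is its timing relative to EPIC. Add a sensitivity analysis restricted to comparators with a pre-ADT baseline.
3. Correct the statement in the Phase 2 sample size rationale that the phases differ only in PSMA result and Decipher score.
4. Reconcile inclusion 11d with exclusion 8, so that it is clear how the testosterone criterion applies to patients who have started ADT.

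**Cost.** A few sentences in protocol and SAP, and one recorded item. All patients stay in the primary model. The group contrast then rests mainly on comparators without early ADT: of 153 per arm, 153 × (1 − *p*) = about 111, 90 or 69 in the three cases. ANCOVA power is then about 87% to 90%, above the planned 83%, though in the low case it is no better than leaving the small bias in place (87% against 88%). The more baselines are taken before ADT under item 1, the less precision item 2 costs.
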